After validation, the American Society of Gastrointestinal Endoscopy defined guidelines for Preservation and Incorporation of Valuable endoscopic Innovations (PIVI) for real time endoscopic assessment of the histology of diminutive polyps.¹⁴ This guideline defines that a technique should have > 90% agreement for post polypectomy surveillance and a negative predictive value of > 90%. In expert hands, the NICE classification for polyps meets these PIVI criteria, however this could so far not be confirmed outside an expert setting.^{15–17}

We are currently training a deep learning algorithm not only for polyp detection, but also for polyp characterization. Preliminary results show an accuracy of about 70% - 75%. To further optimize this system's performance, additional images and videos are necessary. Therefore, we would like to take the opportunity during the current study to collect images and videos of some of the detected polyps. With the obtained data we would like to further develop the AI tool for characterization of colonic polyps.

3. Aim

The primary aim of the current study is to further prospectively validate a computer-aided detection tool for colorectal polyp detection and evaluate its technical performance and feasibility in daily clinic. In addition, we want to use the obtained data for further development of an AI tool for characterization of colonic polyps.

4. Definitions

Positive detections:

- False positive detection: The AI-tool indicates a structure that is not a polyp (eg. Air bubbles, stools, tools, fold, ...). We further specified three possible types of false positive detections:
 - (1) Clinically irrelevant false positive detections

These are detections that are obviously false and do not need further or close-by inspection by the endoscopists and can be readily recognized by the trained second observer.

We defined this type of false positive detections in 6 subdivisions:

- 1) Stool remnants: hard or soft stools, remnants of pills or vegetables
- 2) Air bubbles
- 3) Anatomical structures: ileocaecal valve, appendix
- 4) Diverticulum: inverted or non-inverted
- 5) Instruments: all possible accessory instruments (e.g. forceps, needle, snare, ...)
- 6) Vascular structures: all vascular structures (venes or arteries), hemorrhoids
- (2) Clinically relevant false positive detections

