These are detections that could not be classified as a an obviously false positive at first sight and which is indicated by the endoscopists as a side that needs further inspection. In case this is not spotted by the endoscopists, the second observer will ask the endoscopists to perform a second or close-by inspection for better evaluation, not showing endoscopic evidence of a polyp

We subdivided this type of false positive detections in 3 subdivisions:

- 1) (Thickened) fold
- 2) Other: mucosal lesions different from normal colonic mucosa
- 3) Not relocated: the detection could not be relocated for additional endoscopic inspection
- (3) Other false positive detections

This is every other false positive detection that does not fit any other class and does not need a second or close-by inspection.

 True positive detection: The AI-tool detects a mucosal lesion that is endoscopically diagnosed to be a polyp at first sight (detected by the endoscopist) or after second and close-by look (if initially missed by the endoscopist).

If in case of doubt the endoscopist takes a biopsy to rule out a polyp, this detection will be considered as a true positive detection by AI.

Negative detections:

- False negative detection: Every polyp that is found by the endoscopist and is not detected by the AI tool before the attempt of endoscopic optical diagnosis. On detection of a polyp, the endoscopist will use a standardized verbal action (ask "Did the system detect the polyp as well?"), to inform the second observer about the detection. Immediately the second observer hits the detection button on the AI system. This is a button that initiates timelimited indicator on the AI coupled screen for 1 second. If no detection is made by the AI system during that time, the endoscopically found polyp is to be considered as a false negative detection for the AI system.

5. Endpoints

Primary endpoint

Total polyp detection during single pass colonoscopy by the artificial intelligence tool in comparison to polyp detection by the endoscopist with endoscopic diagnosis as a gold standard.

Secondary endpoints

- 1. Total polyp detection during single pass colonoscopy by the artificial intelligence tool in comparison to polyp detection by the endoscopist with histological diagnosis as a gold standard.
- 2. The number of extra detected polyps by artificial intelligence with the endoscopic diagnosis as a gold standard.

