- 3. The number of extra detected polyps by artificial intelligence with the histological diagnosis as a gold standard.
- 4. The endoscopist's polyp miss rate defined as the additional detection of polyps during colonoscopy
- 5. The false positive rate during clean withdrawal.

Exploratory endpoints

- 1. Correlation between the Boston Bowel Preparation Score and the number of false positive detections during colonoscopy.
- 2. Correlation between the endoscopist's historical adenoma detection rate and the number of extra detections and false negative detections by the artificial intelligence system.
- 3. Correlation between the polyp size and number of false negatives and additional detections.
- 4. Correlation between the Paris classification and the number of false negatives and additional detections.

- 5. Correlation between the total number of polyps per colonoscopy and additional detections.
- 6. Correlation between the experience of the endoscopist and additional detections.

6. Study Design

This is an investigator-initiated multicentre non-randomized prospective interventional trial to validate the performance of a novel state-of-the-art computer-aided diagnostic (CAD) tool in polyp detection implemented as second observer during routine diagnostic colonoscopy and to evaluate its feasibility in daily endoscopy. Consecutive patients referred for a screening, surveillance or diagnostic colonoscopy will be included. After standard bowel preparation with PEG based solutions, patients will undergo a standard colonoscopy performed by an endoscopist with moderate to high adenoma detection rate (ADR > 20% and < 50%). A second observer, who is not a trained endoscopist, but a person trained for recognition of polyps and endoscopic lesions (see section 8), will follow the procedure on a bedside AI-tool to count the number of detections made by the AI system and categorize the results into positive or negative results as follows (1) true positive, (2) false negative or (3) false positive (detailed description, see section 4).

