When a detection is made by the AI system and this detection can clearly be categorized the endoscopist and second observer do not communicate. In case of a detection of the AI-system that was not seen by the endoscopist or is unclear to the second observer, the second observer will ask to re-evaluate the indicated region to determine whether after second look it is a true positive not detected by the endoscopist or a clinically relevant false positive detection of the AI system since it caused the endoscopist to take an extra action. Endoscopists will inspect perform a standard colonoscopy with a single withdrawal, inspecting each segment only once, except when the second observer asks to reinspect a certain area in case of a clinically relevant AI detection. The different timings in each segment will be separately measured with a built-in chronometer in the artificial intelligence tool. Time measurement will be initiated once withdrawal is initiated in the caecum and will be determined for every specific segment. In case of therapeutic actions, time registration will be paused and restarted after completion of this therapeutic act. Automated time calculation is integrated in the AI system and provides an overview of the real withdrawal time and the performed therapeutic time. The entire procedure is recorded. The practical set-up is shown in figure 2.

[figure not shown]

Figure 2: Basic set-up of the computer-aided diagnostic (CAD) tool as second observer during endoscopy. A patient undergoes a diagnostic colonoscopy performed by an experienced endoscopist (ADR > 20% and <50%), while a second observer watches the by the CAD-analyzed video to count and categorize the indicated detections. There is no communication between the endoscopist and the second observer unless a clinically relevant finding is found by the second observer or a polyp or clinically relevant finding is made by the endoscopists.

7. Study Population

Inclusion criteria

- Age ≥40 years
- Referral for screening, surveillance or diagnostic colonoscopy
- Able to give informed consent by the patient or by a legal representative

Exclusion criteria for study inclusion

- <40 years old
- Referral for a therapeutic colonoscopy
- Known Lynch syndrome or FAP syndrome
- Any contraindication for colonoscopy or biopsies of the colon

- Uncontrolled coagulopathy
- Confirmed diagnosis of inflammatory bowel disease prior to the scheduled colonoscopy
- Short bowel or ileostomy
- Pregnancy

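### AI detections that could not be relocated are counted as false positives although their reference diagnosis was never obtained; they should be an indeterminate class with bounds

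*Combined protocol and SAP*

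**What the plan says.** Section 4 (Definitions) sets the general rule: "False positive detection: The AI-tool indicates a structure that is not a polyp". For the clinically relevant type, if the endoscopist has not spotted the site, the second observer asks the endoscopist to "perform a second or close-by inspection for better evaluation, not showing endoscopic evidence of a polyp". Three subdivisions follow: folds, other mucosal lesions, and "Not relocated: the detection could not be relocated for additional endoscopic inspection".

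Section 6 (Study Design) gives the purpose of the second look: to "determine whether after second look it is a true positive not detected by the endoscopist or a clinically relevant false positive" detection. It names no third outcome. Section 6 also has the observer sort results into true positive, false negative or false positive only.

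The endpoints in Section 5 that bear on this are the primary comparison of AI with endoscopist against endoscopic diagnosis, and these secondary endpoints:

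- number 2: "The number of extra detected polyps by artificial intelligence with the endoscopic diagnosis as a gold standard";
- number 4: "The endoscopist's polyp miss rate defined as the additional detection of polyps during colonoscopy";
- number 5: "The false positive rate during clean withdrawal".

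The whole procedure is video-recorded (Section 6). Neither Section 4 nor Section 10 plans an adjudication of not-relocated detections or a sensitivity analysis for them.

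**The concern.** The subdivision does not meet the definition it sits under. The class requires an inspection with a negative result; the subdivision is described by the absence of that inspection. A missing reference result is therefore recorded as a negative one.

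The detections concerned are not the obvious artefacts. Stool, bubbles, instruments and vessels have their own clinically irrelevant class. A second look is requested only when the endoscopist had not seen the detection or the observer could not classify it. AI-only polyps come from this same stream, so it cannot be assumed that none of the not-relocated detections is a polyp.

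At stake directly is the false positive rate, which is reported as an estimate in its own right. At stake indirectly is the completeness of the three results that depend on confirmed AI-only polyps: the primary difference, the extra detections and the miss rate.

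**Working it through.** **Step 1. What the label changes.** Let F be the false positives with a reference diagnosis or an obvious cause, u the not-relocated detections, and t the unknown number of those u that were polyps (0 ≤ t ≤ u).

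- False positive count under the plan: F + u.
- Count if the truth were known: F + u − t.
- Overstatement: t, which can lie anywhere from 0 to u.

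**Step 2. What the label does not change.** Section 10 takes the polyp as the unit of the McNemar test. Section 4 requires a true positive to be endoscopically diagnosed as a polyp. An unconfirmed detection is therefore not a row of the paired table, and is neither an extra detection nor an endoscopist miss, whether it is called false positive or indeterminate. The t polyps are missing from those results under either label.

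**Step 3. The plan's sample size.** The inputs from Section 10 are accuracies of 97% and 95%, McNemar test, two-sided 5%, power 90%, 2084 polyps. The plan states no discordance, so two assumptions were tried:

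- Independent errors: AI-only 0.97 × 0.05 = 0.0485 (101.1 polyps); endoscopist-only 0.95 × 0.03 = 0.0285 (59.4 polyps). Exact McNemar power at 2084 is 89.95%, so the stated figure reproduces.
- No polyp missed by both: AI-only 0.05 (104.2 polyps); endoscopist-only 0.03 (62.5 polyps). Power at 2084 by the normal approximation is 89.8%.

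Under both, AI-only minus endoscopist-only is 0.02 × 2084 = 41.68 polyps, and the endoscopist misses 0.05 × 2084 = 104.2.

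**Step 4. Illustration of losses from failure to relocate.** Suppose t of the 2084 polyps are AI-only polyps that were not relocated. Then

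- observed difference = (41.68 − t) / (2084 − t);
- observed miss rate = (104.2 − t) / (2084 − t).

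Power is by the normal approximation, first with no polyp missed by both, then with independent errors.

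| t (assumed) | Difference, points | Miss rate | Power |
|---|---|---|---|
| 0 | 2.00 | 5.0% | 90% / 91% |
| 10 | 31.68/2074 = 1.53 | 94.2/2074 = 4.5% | 72% / 73% |
| 21 | 20.68/2063 = 1.00 | 83.2/2063 = 4.0% | 40% / 42% |
| 31 | 10.68/2053 = 0.52 | 73.2/2053 = 3.6% | 15% / 15% |

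At two polyps per patient there are 2084/2 = 1042 patients, so these values of t are one per about 104, 50 and 34 procedures. They are not document figures. By Step 2 the table is the same with or without the relabelling.

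**Step 5. What the bounds would look like.** Suppose instead that 2084 confirmed polyps are analysed at the planned rates and u detections are indeterminate. Counting none as polyps leaves 2.00 points and a 5.0% miss rate. Counting all as AI-only polyps gives (41.68 + u)/(2084 + u) and (104.2 + u)/(2084 + u). For u = 10 that is 51.68/2094 = 2.47 points and 114.2/2094 = 5.5%. For u = 31 it is 72.68/2115 = 3.44 points and 135.2/2115 = 6.4%.

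**Step 6. Scale for the false positive rate.** Section 2 reports one false positive per minute in the pilot. With 6 to 10 minutes of withdrawal (an assumption; the documents give no time), 1042 patients yield 6,252 to 10,420 false positives. If 31 of these were polyps, the total would be overstated by at most 31/6,252 = 0.5% of itself. The share within the clinically relevant class alone cannot be computed, because the plan gives no expected size for that class.

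**The case against.** The strongest case for the plan is that the class measures burden. Section 6 ties the clinically relevant label to the extra action the endoscopist had to take, and a detection that sends the endoscopist looking for something that cannot be found has that cost. Counting unconfirmed alarms against the device is also conservative for a superiority claim. Because *Not relocated* is recorded separately, the rate without it can be derived from planned data. All of this stands. But burden can be reported without declaring the structure a non-polyp, and conservatism for the primary test does not make the false positive rate or the miss rate correct as estimates.

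A reader might also infer three stronger things that the documents do not support.

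- *That the rule turns AI catches into AI errors in the primary comparison and costs power.* Step 2 shows otherwise: the loss arises because the lesion was not found again, and excluding the class from the paired table leaves it where it already is.
- *That nobody looked.* The observer saw the AI indication, and Section 6 has the endoscopist re-evaluate the region, with an express exception to the single inspection for this purpose. What is missing is a confirming look at the structure.
- *That these are the likeliest AI-only polyps.* The documents give no polyp share. The pilot's false positive frequency, and the failure of a directed second look where one took place, point the other way.

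**Conclusion.** The point holds as a definitional contradiction with one direct consequence: secondary endpoint 5 includes detections that have no reference diagnosis, and is overstated by however many of them were polyps. That number is not known. Against all false positives it is probably small under the assumptions of Step 6; within the clinically relevant class it could matter more.

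The related incompleteness of the primary difference, extra detections and miss rate runs against the AI and in favour of the endoscopist. It is real to the extent that any not-relocated detection was a polyp, but it is not an effect of the label and relabelling does not cure it. It can only be bounded. The falls in power in Step 4 show sensitivity to such losses; they are not a predicted consequence of this rule.

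The conclusion assumes that the primary analysis is confined to polyps. Section 10 speaks of accuracy without defining it; if false positives were to enter that measure, the label would reach the primary result too.

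**What to change.** 1. In Section 4, move *Not relocated* out of the false positives into a separate class, *indeterminate (reference diagnosis not obtained)*, and add this third outcome to the second-look description and the list of categories in Section 6.
2. Report the count of indeterminate detections, and include it in the account of procedural burden because each one prompted an extra action.
3. Report the false positive rate with and without the class.
4. Add to Section 10 a sensitivity analysis giving bounds for the primary difference, the extra detections and the miss rate, with all indeterminate detections counted as AI-only polyps and then all as non-polyps.

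The cost is a wording change and a few analysis lines. The observer already counts and categorises every detection, and this subdivision is already separate, so no new data are needed. The downside is that these rates are reported with a range.

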Exclusion criteria for study analysis

- Colonic inflammation of > 30cm during colonoscopy
- Incomplete colonoscopy for any reason
- Incomplete recording or technical failure of the artificial intelligence system

8. Study Procedures

Bowel preparation

Before endoscopy patients will be prepared either at home either in hospital with standard bowel preparation according to local practice in the respective research centers, with an oral polyethylene glycol based regimen and if necessary, with an additional water enema. During endoscopy, all residual stools will be removed from the colonic wall by rinsing with water with or without dimeticon. Every subject's bowel preparation will be scored using the Boston Bowel Preparation Scale (BBPS).

Endoscopy, video recording

Endoscopy will be performed in patients on the scheduled appointment as initially made after selection based on referral. Video recording of the procedure will be initiated to record the patient's number upon the case report form before the endoscope is introduced in the anal canal. Before withdrawal, a picture of the caecum needs to be taken. During withdrawal the bowel should be as maximal inflated as possible for a high-quality inspection. A single pass withdrawal will be applied during inspection.

If a polyp is found, it can be resected after an endoscopist's optical assessment. This endoscopist's optical assessment should include description of the polyp size, location, Paris classification and if possible endoscopic diagnosis of most probable histology (hyperplastic, sessile serrated, adenoma or carcinoma).

If more than 5 polyps with apparent hyperplastic morphology are found in the rectosigmoid, the first 5 polyps will be included for analysis of the AI tool performance and will be resected for histological assessment and inclusion in the study. Any additional apparent hyperplastic polyps in the rectosigmoid exceeding the number of 5 will be discarded from the study for practical reasons. Most of these polyps will be hyperplastic and are clinically irrelevant. Additional separate biopsies of these sometimes many polyps will incur unnecessary costs. The entire procedure needs to be recorded as one video.

Second observer

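### The endoscopist's scripted polyp call asks for the AI result before the optical diagnosis, and no rule withholds a negative answer or makes the call final

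*Combined protocol and SAP*

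**What the plan says.** All of this is in the combined protocol.

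- **Section 4, false negative detection.** An AI miss is a polyp found by the endoscopist and "not detected by the AI tool before the attempt of endoscopic optical diagnosis". On finding a polyp the endoscopist asks "Did the system detect the polyp as well"; the stated purpose is to let the observer know of the finding. "Immediately the second observer hits the detection button on the AI system", which opens a one-second window. With no AI detection in that window, "the endoscopically found polyp is to be considered as a false negative detection for the AI system".
- **Section 5, primary endpoint.** AI detection is assessed "in comparison to polyp detection by the endoscopist with endoscopic diagnosis as a gold standard".
- **Section 8, endoscopy.** "If a polyp is found, it can be resected after an endoscopist's optical assessment". That assessment covers size, location, Paris class and, where possible, likely histology.
- **Section 6, main text.** "When a detection is made by the AI system and this detection can clearly be categorized the endoscopist and second observer do not communicate".
- **Figure 2 legend.** The ban on communication is lifted for a clinically relevant finding by the observer "or a polyp or clinically relevant finding is made by the endoscopists".

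The protocol does not say whether the observer answers the question. It does not say that the endoscopist stays unaware of the AI result until the assessment is recorded, or how to count a called lesion later judged not to be a polyp.

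**The concern.** The person who supplies the reference diagnosis is scripted to ask for the result of the test under study before completing the optical assessment. If the observer answers, an endoscopist unsure about a lesion may let a negative answer settle the matter and drop it. A dropped lesion is no longer a polyp, so it is no longer an AI false negative. It also fits none of the three result categories in section 6 (true positive, false negative, false positive), so it would leave no trace.

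This is review bias on the primary endpoint, in the direction of the superiority claim. The histology-based secondary endpoint would not recover a dropped lesion from which no tissue was taken. The procedures are recorded, but no blinded re-reading of the videos is planned.

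**Working it through.** **1. Order of events for a lesion the endoscopist finds.** Detection, then the question, then the button press and one-second window, then optical assessment, then resection if done. The AI status is known to the observer before the optical assessment begins.

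**2. What the communication rules cover.**

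| Situation at the call | Section 6 silence rule | Figure 2 legend |
|---|---|---|
| AI detected the lesion, clearly categorised | Arguably applies | Communication allowed |
| AI did not detect the lesion | Does not apply, as there is no AI detection | Communication allowed |

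So a negative answer is not withheld by either rule.

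**3. The plan's own figure.** Section 10 gives accuracies of 97% (AI) and 95% (endoscopist), a McNemar test, two-sided 5%, 90% power and 2084 polyps. With d = 0.02 and discordant share s,

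n = [1.96·√s + 1.2816·√(s − d²)]² / d².

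The protocol does not state s.

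- No polyp missed by both: s = 0.05 + 0.03 = 0.08, n = 2098.
- Independent errors: s = 0.97 × 0.05 + 0.03 × 0.95 = 0.077, n = 2019.
- s = 0.0795 gives 2084.

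The stated sample size is reproduced closely and is not in dispute. A lesion found by neither is never recorded, so the first case is used below. The expected discordant polyps are then 0.05 × 2084 = 104 AI-only and 0.03 × 2084 = 63 endoscopist-only (the AI misses).

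**4. Which answers can move the test.** McNemar uses only the discordant cells: z = (b − c)/√(b + c), with b AI-only and c endoscopist-only. A lesion kept after a positive answer was found by both, so it enters neither cell. A lesion dropped after a negative answer leaves c.

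**5. Effect of withdrawals with no true difference.** Assume b = c = 63 and withdraw y AI misses. Then z = y/√(126 − y).

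| y | Share of 63 AI misses | z |
|---|---|---|
| 10 | 16% | 10/√116 = 0.93 |
| 20 | 32% | 20/√106 = 1.94 |
| 21 | 33% | 21/√105 = 2.05 |

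The expected counts cross 1.96 at 21 withdrawals, one third of the AI misses.

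**6. Effect on the error rate.** Expected counts understate the effect because chance variation adds to the shift. Assume instead 96% accuracy each, hence 4% discordant each way (83 vs 83), and let a share w of AI misses be withdrawn. The polyp total and both discordant shares are rescaled for the lost lesions, and

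P(AI superior) ≈ Φ{[√N·d − 1.96·√s]/√(s − d²)}.

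| w | Polyps withdrawn | P(false AI win) |
|---|---|---|
| 0 | 0 | 2.5% |
| 5% | about 4 | 5.1% |
| 10% | about 8 | 9.7% |
| 20% | about 17 | 27% |
| 30% | 25 | 56% |

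If the planned 97% vs 95% is true, w = 10% (about 6 polyps) raises observed AI accuracy from 97.0% to 97.3% and apparent power from 89.8% to 96.6%.

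Every value of y and w here is an assumption. The documents give no figure for how often a call would be reversed.

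**The case against.** The strongest reply is that the polyp judgement comes before the question. The call is triggered by detection of a polyp, and section 4 counts a lesion diagnosed as a polyp at first sight as endoscopist-detected. The later optical assessment describes the polyp and has no outcome for *not a polyp*. The one-second rule already classes a called polyp as an AI false negative, and there is no retraction step. The question serves to inform the observer, whose prescribed response is to press a button, not to speak.

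Most of this stands, and it rules out several stronger readings that a reader might infer:

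- *The endoscopist is told the AI result by design.* No section instructs the observer to answer. The question invites disclosure but does not order it.
- *The protocol lets AI misses be withdrawn.* It does not provide for this. Withdrawal would need an endoscopist to reverse a voiced call; the gap is only that nothing says the call is final.
- *Positive answers inflate AI superiority.* They add concordant polyps, which McNemar ignores.
- *The optical histology is compromised as well.* The answer would say only whether the AI detected the lesion. Section 2 describes characterisation as still being trained, and in section 8 a mismatch with pathology only triggers further pathology review.

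It is also fair to say that some lesions dropped after a negative answer may truly not be polyps, and that such an answer could equally prompt closer inspection. What the reply does not remove is a scripted question, put by the person who sets the reference, with no rule on what may be said in return.

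**Conclusion.** The point holds in a limited form. The wording of the call opens an avoidable route to review bias on the primary endpoint. It works only through doubtful lesions dropped after the endoscopist hears that the AI did not flag them, and its direction favours AI.

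The size cannot be established. From 63 vs 63, about a third of AI misses would have to be withdrawn for the expected counts alone to reach significance, and 16% would not do it. On the separate 83 vs 83 assumption, 10% withdrawn would raise the false-positive rate in favour of AI from 2.5% to 9.7%. Both sets of figures assume no double misses, no true difference and a reversal rate for which the documents give no evidence. They show that a test resting on roughly 130 to 170 discordant polyps is sensitive to small losses, not that such losses will occur.

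This does not invalidate the design or the sample size. It should be changed because the protection costs so little.

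**What to change.** In section 4 and the observer training:

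1. Replace the question with a neutral one-way call, for example the single word *polyp*. It informs the observer just as well.
2. State that every voiced call stays in the primary comparison as an endoscopist detection, with the AI status fixed at the button press.
3. State that the observer does not disclose the AI status until the endoscopist has dictated polyp or not polyp and the optical assessment. Align the section 6 silence rule and the Figure 2 legend with this.
4. Record any retracted call with its AI status, and report the number by AI status.

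Keeping every voiced call may retain a few lesions that are not polyps as AI misses; the retraction count shows how many are in question.

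The cost is a small change to the script and observer training, plus one CRF field. The sample size, staffing and procedures do not change.
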